To Study the Efficacy of Teriparatide in Improving Remodeling of Foot Bones in Chronic Charcot Neuroarthropathy in Patients With Diabetes Mellitus.

Protocol date: 1/1/2016

NCT : ABAR-1072013

Patients and methods:

People with type 2 diabetes and inactive charcot neuroarthropathy of foot attending the diabetic foot care unit of department of endocrinology at Post Graduate Institute of Medical Education and Research (PGIMER), Chandigarh were prospectively enrolled in the study. An informed and written consent was obtained from all the participants and the Institute Ethics Committee approved the study protocol. The diagnosis of inactive charcot foot was confirmed on clinical and radiological examination (Eichenholtz's classification) (16) of the foot. The inactive charcot foot was suggested by the absence of signs of activity i.e lack of temperature difference between two feet (measured using infrared thermometer) and no T2 hyperintensity on Magnetic resonance imaging (MRI) and/or the presence of deformities like pes-planus or rocker bottom foot with a prior history of active charcot neuroarthropathy (12 months prior) or scrutiny of treatment records revealed active charcot foot (total contact cast) in recent past. The patients with active charcot neuroarthropathy (within 12 months), active on inactive charcot neuroarthropathy, osteomyelitis of foot bones, concurrent peripheral vascular disease, presence of non-healing ulcer or a history of foot ulcer in the past 12 weeks, presence of vascular calcification on foot X-ray, osteoporosis at lumbar spine or hip (defined as T Score \leq -2.5), renal failure (eGFR < 60 ml/min), previous/prevalent bone malignancy, previous malignancy with metastasis to bone, received teriparatide or bisphosphonates earlier (within past 12 months), primary hyperparathyroidism, pregnant women were excluded from the study. Patients were randomized by computerized random program into two groups to receive Teriparatide (T group) 20 μ g between 8-9 pm or placebo (P group) subcutaneous daily. The clinician in-charge, the participants, radiologist and the nuclear medicine specialists were unaware of the treatment group allocation. The adherence to teriparatide or placebo was ensured by telephonic call and collecting empty cartridges on subsequent visits from the participants. The standard treatment for inactive charcot neuroarthropathy by advice for effective offloading with modified footwear were provided to all patients.

Regional ^{18}F -PET/CT images of the feet were acquired at baseline, 3 and 12 months using a dedicated PET/CT scanner (Discovery STE16 or 710, GE Healthcare, Milwaukee, WI, USA) in 3-D mode at 1, 2 and 3 hours after intravenous injection of 185MBq (5mCi) of Na^{18}F -fluoride. The CT variables for acquisition were 140kV, 40mA & pitch of 1.375:1.

Reconstructed trans-axial, coronal and sagittal images were viewed on advantage workstation adw 4.6. Semi quantitative analysis for standardized uptake value (SUVmax) was done by drawing the ROIs at the fore, mid and hind foot regions and compared with the baseline ^{18}F -PET/CT for change in SUVmax. Increased tracer uptake in the fore, mid and hind foot in relation to the background normal bone was taken as abnormal. A $\text{SUVmax} \geq 2.5$ at 2 hours was considered significant based on our prior experience [15].

Outcome Measure:

Primary outcome measure was the change in SUVmax on ^{18}F -PET/CT compared to baseline. Bone turnover markers, foot BMD (ROI) and foot inclination angles were the exploratory variables.

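### The plan names no between-arm, baseline-adjusted comparison of SUVmax change; simple change is valid between arms but less precise, and a within-arm test would mislead

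*Combined protocol and SAP*

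**What the plan says.** All references are to the combined protocol and SAP.

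- **Outcome Measure:** "Primary outcome measure was the change in SUVmax on ^{18}F -PET/CT compared to baseline". No test, model, covariate, primary visit or direction of benefit follows.
- **Nuclear Imaging:** scans are taken at baseline, 3 and 12 months, at 1, 2 and 3 hours after injection. Uptake is measured by "drawing the ROIs at the fore, mid and hind foot regions and compared with the baseline" scan. The only uptake threshold is a reading rule: "A $\text{SUVmax} \geq 2.5$ at 2 hours was considered significant based on our prior experience [15]". It is not an entry criterion.
- **Patients and methods, entry:** inactivity is suggested by "lack of temperature difference between two feet (measured using infrared thermometer) and no T2 hyperintensity on Magnetic resonance imaging (MRI"), and/or by deformity "with a prior history of active charcot neuroarthropathy (12 months prior"), or where "scrutiny of treatment records revealed active charcot foot (total contact cast) in recent past". Active disease within 12 months is an exclusion. No upper limit on time since activity is given.
- **Patients and methods, allocation:** "Patients were randomized by computerized random program into two groups", teriparatide or daily subcutaneous placebo. Stratification is not mentioned. The clinician, participants, radiologist and nuclear medicine readers are blinded, and offloading advice goes to everyone.

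**The concern.** Nothing in the plan restricts, balances or adjusts for the starting value of its only primary outcome. Patients may differ widely in residual uptake, and a foot that starts high has more room to fall than one near normal bone, whatever the treatment. Three things follow for an analysis of simple change:

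- Variation explained by baseline stays in the error term, so the arm difference is less precise than the same data allow.
- If one arm happens to start higher, that arm tends to show the larger fall.
- The outcome is worded as a comparison with baseline rather than between arms. If it were tested inside the teriparatide arm alone, the natural course of the disease would be mixed with the effect of the drug. The plan does not say whether a fall or a rise is the hoped-for result, so settling could either mimic or mask an effect.

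**Working it through.** **Inputs.** The documents give no sample size, SD, correlation, alpha or power, so there is no planned figure to reproduce. Assumed throughout: correlation r between baseline and follow-up SUVmax from 0.3 to 0.9 and, except in step 2, the same SD s at both visits.

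**1. Precision.** Variance per patient is 2s²(1-r) for simple change and s²(1-r²) after baseline adjustment. The ratio is 2(1-r)/(1-r²) = 2/(1+r). For an illustrative difference of 0.8 SD (two-sided 0.05, 80% power, normal approximation), n per arm = 2(1.96+0.84)²/0.8² times the variance in units of s², rounded up.

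| r | Variance ratio | n per arm, simple change | n per arm, adjusted |
|---|---|---|---|
| 0.3 | 2/1.3 = 1.54 | 35 | 23 |
| 0.5 | 2/1.5 = 1.33 | 25 | 19 |
| 0.7 | 2/1.7 = 1.18 | 15 | 13 |
| 0.9 | 2/1.9 = 1.05 | 5 | 5 |

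**2. Unequal SDs.** If the follow-up SD is k times the baseline SD, the ratio is (1+k²-2rk)/(k²(1-r²)). At r = 0.5:

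- k = 0.7 (spread shrinks as uptake settles): (1+0.49-0.70)/(0.49×0.75) = 2.15
- k = 1.3: (1+1.69-1.30)/(1.69×0.75) = 1.10

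**3. Chance imbalance.** Given a baseline difference d between arms, the expected difference in simple change under no drug effect is -(1-r)d. One standard error of d is √(2/n) SD. With an assumed 20 per arm that is √(2/20) = 0.316 SD, so a 1-SE imbalance shifts the contrast by 0.22, 0.16, 0.10 and 0.03 SD at r = 0.3, 0.5, 0.7 and 0.9.

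For the nominal 5% test, work in units of √(2/n). The contrast then has mean -(1-r)z and SD √(1-r²), and the critical value is 1.96√(2(1-r)), where z is the imbalance in SEs.

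| r | Rejection rate, z = 0 | z = 1 | z = 2 |
|---|---|---|---|
| 0.3 | 0.015 | 0.046 | 0.168 |
| 0.5 | 0.024 | 0.048 | 0.134 |
| 0.7 | 0.034 | 0.049 | 0.101 |
| 0.9 | 0.044 | 0.050 | 0.067 |

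The test is conservative when the arms happen to match and liberal when they do not. Averaged over randomisation it is correct.

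**4. Overall behaviour when uptake is settling.** A simulation with no drug effect checked this, with every setting assumed: 12 to 60 months since activity; background SUV 2 plus a patient-specific excess decaying at 0.01 or 0.03 per month; measurement SD 0.5; follow-up 12 months after baseline; 10, 20 or 30 per arm; 6,000 runs per setting.

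- Between arms, simple change: type I error 0.047 to 0.052, mean bias within 0.005 SUV.
- Between arms, adjusted for baseline: type I error 0.049 to 0.058.
- When one arm started more than 1 SE higher: simple change showed a spurious -0.16 to -0.42 SUV; the adjusted difference stayed within 0.01 of zero.
- Standard errors at 20 per arm: 0.240 against 0.210 at the slower decay, a variance ratio of (0.240/0.210)² = 1.31; and 0.279 against 0.192 at the faster decay, a ratio of 2.11.

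**5. Within-arm test.** In the same null trials, testing the teriparatide arm's change against zero declared an effect in 51% to 99.8% of runs.

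**The case against.** A reader might infer that, because feet can enter at any stage of quiescence, continuing settling would be counted as treatment effect. The documents do not support that for a comparison between arms. The trial is randomised, placebo-controlled and blinded down to the image readers, so settling is expected equally in both arms and cancels; step 4 confirms it. The reading holds only for a within-arm test. The wording permits one but does not prescribe it.

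A reader might also infer that the sponsor chose an unadjusted analysis. The text defines a variable and names no model, and change from baseline can be analysed with baseline as a covariate. The defect is silence, not a wrong choice.

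Three further objections stand:

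- The shift in step 3 is conditional on an imbalance having arisen. It is not systematic bias, and the standard error already allows for it.
- At r = 0.9 the variance penalty is only 5%, and in a small trial estimating the slope could use that up. The size of the gain is therefore unknown.
- Time since the active episode is not shown to be available. The exclusion requires only that no activity occurred within 12 months, and the clinical details listed for recording include no episode date. The documents also give no data on how uptake declines with time.

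The absence of an uptake threshold at entry does not in itself cause regression to the mean in the group as a whole; selecting on high uptake would.

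None of this removes the case for adjustment. Baseline SUVmax must be collected, since change cannot be computed without it, and naming the model in advance prevents a choice after the results are seen.

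**Conclusion.** The point holds as one of precision and of an unspecified contrast, not as a threat to the validity of a randomised comparison. With equal SDs, simple change carries 5% to 54% more variance than the baseline-adjusted difference over r = 0.9 to 0.3. The penalty is larger if spread shrinks at follow-up and smaller if it grows. A chance baseline imbalance, if it occurs, moves the simple-change contrast by -(1-r) per unit, while overall type I error is held. The serious error, reading settling as a drug effect, arises only if the conclusion rests on change within the teriparatide arm, and the plan should rule that out. The correlation, SDs, sample sizes and decay rates are all assumptions, because the documents give none.

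**What to change.** Keep SUVmax change as the primary outcome and add to the Outcome Measure section that:

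- the efficacy conclusion rests on the between-arm difference from a linear model with treatment and baseline SUVmax, the baseline value coming from the same foot region and uptake time as the follow-up value;
- baseline SUVmax is shown by arm;
- within-arm changes are descriptive only.

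Matching the covariate requires the plan to say which of the three regions, three uptake times and two follow-up visits is primary; at present none is named.

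Time since the active episode may be added as a supportive covariate where it is reliably dated. The entry wording that accepts active disease shown by treatment records, without a time limit, and the exclusion of active disease within 12 months must be reconciled.

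The cost is a few sentences and one degree of freedom, with one more if the supportive covariate is used. The main model needs no new scans, visits, patients or data.
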